8.3.2 Secondary endpoints

- 8.3.2.1 Strength of association between µCor measurements and clinically related heart failure events.
- 8.3.2.2 Strength of association between µCor measurements and subject reported symptoms.
- 8.3.2.3 Descriptive statistics around hospital readmission rate, physician visit rate, and outpatient clinic visit rate during the study period.
- 8.3.2.4 Descriptive statistics around mortality, heart failure related events, quality of life (QoL), and health care utilization data at 6 months and on year post enrollment.

8.4 Statistical Methods

Concerning the primary endpoint, investigator engagement will be assessed through the number of data updates delivered by the µCor subject management system, frequency of medication changes based on µCor data, frequency of lifestyle modifications that are recommended to the subject, frequency of medication changes based on symptoms reported by subjects or from subject incidental findings, and frequency high µCor measurements that are reduced below threshold levels after medication was titrated or lifestyle modifications were recommended.

Concerning the secondary endpoints, associations between µCor measurements and clinically related heart failure events will be assessed through sensitivity/specificity analyses. µCor measurements at both baseline (first day of fitting) and the time of heart failure admission will be compared among subjects with or without heart failure related events using t-tests or other appropriate statistical methods.

For primary, secondary, and safety endpoints, descriptive statistics and qualitative analysis will be performed as appropriate. Descriptive statistics will include frequency of data updates delivered by the µCor data system, frequency of physician action to µCor data or µCor data updates, and physician action events as a percentage of all data updates received.

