6.1.3 Definitions

An acute heart failure event requiring medical management, and a heart failure related clinical event, is defined as a hospitalization, emergency room visit, observation unit visit, or unplanned clinic visit where medical management or treatment for HF related pulmonary congestion is administered.

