 - Any physician visits, both planned and unplanned
 - Any hospitalization, including heart failure hospitalization
 - Any emergency room visits
 - Any symptoms, including syncope, dyspnea, palpitations and chest pain
- 6.2.4.4 A weight measurement will be obtained.
- 6.2.4.5 Subjects will be given a physical assessment
- 6.2.2.6 Daily cardiac medications taken by the subject will be reviewed and compared to the last listed cardiac medications documented by the study. Any new cardiac medications or changes in medication will be recorded (i.e. dosage changes or new medications administered)
- 6.2.4.7 Subjects will be asked if they would like to continue wear for an additional 90 days. If the subject had experienced a heart failure related clinical event within the previous 90 days, the subject will also be given the option to continue wear for 30 days following the most recent heart failure event.

6.3 *Unscheduled Visits*

- 6.3.1 Clinic visits, ED visits, and hospitalizations that have resulted from a device data update will be defined as unscheduled events. Separately, all heart failure related contact with the subject either initiated by the subject or the site will be defined as an unscheduled visit. Heart failure contact includes, but is not limited to, contact with the subject concerning new or worsening heart failure symptoms such as dyspnea, pedal edema, and shortness of breath.
- 6.3.2 Upon receiving a data update, which will be initiated when the day averaged TFI readings have exceeded for three consecutive days a threshold defined by three standard deviations of baseline TFI, the site study team will reach out to the subject within 24 hours. The data update will be delivered to the site via either fax, email, or phone call.
- 6.3.3 The investigator will make a decision whether to contact the subject or take no further action based on the data update, and document the reason. There will be a structured interview between the investigator and subject. The investigator will have access to a report that displays the device data.
- 6.3.4 If the subject is called after device data update, the subject's symptoms and recent history will be documented, and a medical decision, within the context of standard of care,

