will be given to the patient. The medical decision may include assessment with no action required, adjusting or starting new medication, requesting an office visit, requesting an ED visit, requesting a lifestyle/diet change, requesting a hospital admission, or no change at all. All decisions will be documented.

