8.3 Endpoint Assessment

8.3.1 Primary endpoint

The primary endpoint will be assessed in an observational nature through the frequency and characterization of site engagement with uCor data. The assessment will be made study-wide in addition to geographic regions. Site engagement will be assessed through the following:

- 8.3.1.1 The number of data updates received by the µCor subject management system.
- 8.3.1.2 An assessment of the approximate time spent reviewing data reports assessed within sites and across sites. Investigators will be asked, for each report, whether they spent 0-5min, 5-10min, or greater than 10 minutes reviewing the data.
- 8.3.1.3 The number of medication changes based on µCor data and the number of lifestyle modifications were recommended to the subject.
- 8.3.1.4 The number of medication changes based on symptoms reported by subjects or from subject incidental findings.
- 8.3.1.5 The number of times high µCor measurements were reduced below threshold levels after medication was titrated or lifestyle modifications were recommended.

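### Section 8.4 scores µCor measurements against heart failure events without separating the events that µCor data prompted, so the results for objective 2.2.1 mix device accuracy with site behaviour

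*Combined protocol and SAP*

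**What the plan says.** **Analysis.** Section 8.4 says that links between µCor readings and "clinically related heart failure events will be assessed through sensitivity/specificity analyses". It adds that readings on the first day of fitting and at "the time of heart failure admission will be compared among subjects with or without heart failure related events", by t-tests or other methods. Section 8.5 (additional analyses) is marked NA.

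**Event definition.** Objective 2.2.1 points to section 6.1.3, where an event is a "hospitalization, emergency room visit, observation unit visit, or unplanned clinic visit where medical management or treatment for HF related pulmonary congestion is administered". What prompted the visit plays no part. Section 3.1.1 treats a visit as unplanned if the subject had not planned it more than 48 hours ahead.

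**Site action.** Under 3.1.1 and 6.3.2, an update goes to the site when day-averaged TFI stays above a three-standard-deviation threshold for three consecutive days. Besides medication changes, the decisions listed in 6.3.4 include "requesting an office visit, requesting an ED visit, requesting a lifestyle/diet change, requesting a hospital admission".

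**Labels.** Section 6.3.1 says: "Clinic visits, ED visits, and hospitalizations that have resulted from a device data update will be defined as unscheduled events". It gives other contacts about heart failure, whoever starts them, a second label (unscheduled visit). Neither label is used in 6.1.3, 8.3.2 or 8.4.

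**Related descriptive items.** Section 8.4 reports "physician action events as a percentage of all data updates received". Section 8.3.1.5 counts the times high readings "were reduced below threshold levels after medication was titrated or lifestyle modifications were recommended". Neither is linked to the sensitivity/specificity analysis.

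**The concern.** Sensitivity and specificity need a reference standard that the test does not influence. Here TFI can influence it in two ways.

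1. An update may lead the site to request a visit at which congestion is treated. That visit is then an event, so the update has helped to create its own true positive.
2. An update may lead to treatment that prevents an event. If the positive test is the update or something close to it, that correct warning is scored as a false positive.

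A reader of the results could not tell how much of the reported sensitivity came from visits the device prompted, or how many false positives were warnings that were treated. TFI is most exposed because it triggers the updates. Rhythm is less exposed, since 6.7 keeps ECG out of real-time and update reports. However, every measurement is compared across the same event groups, so none is wholly outside the problem.

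**Working it through.** **No figure to reproduce.** The plan gives 300 subjects and 80 sites, but no event rate, expected sensitivity or specificity, or rate of site action. Every rate below except N is an assumption.

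**Inputs.** N = 300 (section 5.2). Assumed: E = 75 subjects with an impending event; f = 0.2, the share of the other 225 who get an update; s, the true sensitivity; v, the share of false updates that become treated visits counted as events; a, the share of detected impending events that are averted. The positive test is taken as any update during wear, one classification per subject, ignoring timing.

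**Formulas (all events counted).**
- TP = sE(1−a) + vf(N−E)
- FN = (1−s)E
- FP = f(N−E)(1−v) + sEa
- TN = (1−f)(N−E) = 180

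Worked case, s = 0.2, v = a = 0.1: TP = 13.5 + 4.5 = 18; FN = 60; FP = 40.5 + 1.5 = 42. Sensitivity = 18/78 = 23%, specificity = 180/222 = 81%, odds ratio = (18×180)/(60×42) = 1.3.

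| True device | v | a | TP/FN/FP/TN | Sens./spec. | Odds ratio |
|---|---|---|---|---|---|
| No information, 20%/80% (OR 1.0) | 0.05 | 0 | 17.25/60/42.75/180 | 22%/81% | 1.2 |
| | 0.1 | 0.1 | 18/60/42/180 | 23%/81% | 1.3 |
| | 0.3 | 0.3 | 24/60/36/180 | 29%/83% | 2.0 |
| | 0.3 | 0 | 28.5/60/31.5/180 | 32%/85% | 2.7 |
| | 0 | 0.3 | 10.5/60/49.5/180 | 15%/78% | 0.6 |
| Working, 40%/80% (OR 2.7) | 0.1 | 0.1 | 31.5/45/43.5/180 | 41%/81% | 2.9 |
| | 0.3 | 0.3 | 34.5/45/40.5/180 | 43%/82% | 3.4 |
| | 0.5 | 0 | 52.5/45/22.5/180 | 54%/89% | 9.3 |
| | 0 | 0.5 | 15/45/60/180 | 25%/75% | 1.0 |

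**Direction.** The effects balance when vf(N−E) = asE. That is 45v = 15a (v = a/3) for the no-information device and 45v = 30a (v = 2a/3) for the working one. Above the balance point the figures are inflated; below it they are deflated.

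**Other inputs.** For the no-information device at v = a = 0.3, the odds ratio is 3.2 with E = 45 and 1.5 with E = 105. For a 60%/80% device with 90 impending events among 300, sensitivity runs from 42.9% (v = 0, a = 0.5) to 67.6% (v = 0.5, a = 0), and specificity from 70.9% to 88.9%.

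**Comparisons by event status.** In the no-information case with v = a = 0.3, the event group has 24 + 60 = 84 subjects. Of these, 0.3 × 45 = 13.5 (16%) had no impending event and entered through a prompted visit, while 0.3 × 15 = 4.5 left it because their event was averted. First-day readings cannot be changed by later site action, but the groups they are compared across can. No size is given for the admission-time comparison, because 8.4 does not say which reading represents a subject without an admission.

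**Recoding prompted events as non-events is not a clean repair.** Let p be the share of the remaining detected events reached through a site request. Then TP = sE(1−a)(1−p) and FP = f(N−E) + sEa + sE(1−a)p. For the working device at a = p = 0.3: TP = 14.7, FN = 45, FP = 45 + 9 + 6.3 = 60.3, giving 25%/75%. The device now looks uninformative.

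**The case against.** The case against is substantial.

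- **The study is meant to be open.** Sites are supposed to act on the data, the objective asks for correlations, and there is no performance target. This stands, and it limits the stakes.
- **At plausible rates the shift is small.** An event needs treatment for pulmonary congestion, the site assesses symptoms first, and a drug change by phone is not an event. Some prompted visits will also be genuine detection. At v = a = 0.1 the shift of 1 to 3 points is well inside sampling error: with 75 events the 95% half-width is 1.96√(0.2×0.8/75) = 9 points at 20% sensitivity, and 1.96√(0.4×0.6/75) = 11 points at 40%. This stands for size. Sampling error is reported through an interval, however, whereas this mixing would not be visible.
- **The protocol already labels update-prompted visits and documents decisions.** True (6.3.1, 6.3.3, 6.3.4, 6.6), and the case report form is not among the documents, so it may already capture origin. The gap is that 8.4 does not use the label.

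Three stronger readings are tempting and are not supported:

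- A reader might infer that every visit a site requests becomes an event. A requested clinic visit counts only if it is unplanned under the 48-hour rule in 3.1.1, which limits v. Hospitalizations, ED visits and observation unit visits carry no such limit.
- A reader might infer that one update is scored both as engagement under 8.3.1.5 and as a false positive under 8.4. Section 8.3.1.5 counts readings that fall below threshold and mentions neither updates nor averted events, and 8.4 does not define a positive test. The overlap is possible, not stated.
- A reader might infer that TFI accuracy will be overstated. The averting effect pulls the other way, and no rates are given.

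**Conclusion.** The concern holds as a gap in the analysis plan. Followed as written, section 8.4 yields accuracy figures for TFI that combine what the device detects with what sites do about it. The mechanism through false positives is conditional on the positive test being the update threshold or a related TFI rule. The comparisons of subjects with and without events are affected through group membership for every measurement, including the baseline comparison.

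Net direction and size are unknown. Under the assumed rates the shift in sensitivity is about 1 to 3 points when both effects are at 10%. The large distortions (a useless device at an odds ratio of 2.7, a useful one at 1.0 or 9.3) need higher rates with only one effect operating. They show what is possible, not what is expected.

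Visits prompted by the weekly data review are an inference: 6.6 has care changes documented but does not mention visit requests. The primary engagement endpoint is not affected. This is a should-fix point on a secondary objective with no decision rule attached.

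**What to change.** 1. Record the origin of each heart failure event: prompted by a data update, prompted by other review of µCor data, or independent. Build it on the 6.3.1 label and the decisions already documented, unless the case report form already holds it.
2. In section 8.4, state the positive-test rule and the time window linking a test result to an event.
3. Beside the all-events sensitivity/specificity, tabulate test result against no event, independent event and µCor-prompted event.
4. Show the baseline and admission-time comparisons for all events and for independent events only.
5. Tabulate updates followed by a care change and no event.
6. Label any analysis that drops or recodes prompted events as a sensitivity analysis.
7. State that all accuracy figures are conditional on care guided by the data.

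The cost is at most one case report form field, some wording and a few tables. The downsides are fewer events per stratum and some judgement in assigning origin, given weekly calls and other site contact. The three-way table discloses the dependence but does not remove it, because origin does not show whether a prompted event would have happened anyway, and averted events remain unseen.

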3.1 General Design

3.1.1 Study Description

Subjects meeting the inclusion/exclusion criteria will wear μ Cor for up to 90 days from the day of fitting. 300 total patients will be enrolled. Subjects will be fitted with μ Cor during discharge of a heart failure related hospitalization or within a clinic visit that has occurred within 10 days of a heart failure related hospitalization. The μ Cor fitting will mark day 0 of the study. An LVEF measurement will be recorded during enrollment or within 30 days post enrollment if an LVEF measurement has not been recorded within 30 days prior to enrollment. Any LVEF will qualify for the study. An investigator assessment will be performed during all clinic visits. The assessment template is shown in Appendix A.

Subjects will be given a diary at enrollment that will ask them to rate their degree of specific symptoms of heart failure such as shortness of breath and fatigue as well as mark any heart failure related clinical events or medication changes that have occurred since the last entry. The subject diary is shown in Appendix A.

Phone calls will be based on weekly data reviews or data updates. A review of the data will be conducted by the site before the weekly phone call and the most recent (Transthoracic Fluid Index) TFI will be recorded. The subject will receive a study based weekly phone call asking the subject about any recent heart failure related clinical events or change in heart failure symptoms. The weekly phone calls will continue if the subject has stopped wearing the device. During the weekly phone call the subject will be reminded to fill out the daily diary. No phone calls will be given on the week where there is a study follow up visit.

A review of the data will be conducted by the site before the office visit and the most recent TFI will be recorded. Study face to face follow up visits will occur at day 30, day 60, and day 90. There will be no follow up visit if the subject has stopped wearing the device. During follow up visits the subjects will be asked about any heart failure related clinical events or change in symptoms that have occurred since the last follow up.

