4.1 Inclusion Criteria

The following criteria will be used to include subjects in the study: An acute heart failure event requiring medical management is defined in section 6.1.3. The index hospitalization and six month prior event must have started two weeks apart from one another.

4.1.1 Subjects hospitalized for acute decompensated heart failure and enrolled in the study within 10 days post-hospital discharge.

4.1.2 Subjects who have had an acute heart failure event requiring medical management in the previous 180 days of index hospitalization admission. This acute heart failure event admission must be at least 2 weeks apart from the event admission in 4.1.1

4.1.3 Subjects 21 years of age or older on the day of screening.

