6.4 Long-term Clinical Outcome Assessment

The subject will receive a follow up phone call 6 months (180 days) and 1 year (365 days) from the enrollment date to assess for mortality status, heart failure related clinical events that have occurred since the end of μCor wear, and any health care utilization that has occurred since the end of μCor wear. A chart review will be performed during both of these calls as well. Subjects will answer mailed heart failure questionnaires and mail the questionnaires back to the site. These follow-up calls must occur within +/- 2 weeks of the scheduled call.

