7.3 Dispensing, Storage and Return

7.3.1 Dispensing of Study Device

Sites Located Within the United States

The sponsor will be responsible for dispensing the study device. In order to initiate device dispensing in a timely matter, the site will inform the sponsor of subject enrollment on the same date as enrollment.

The sponsor will initiate a device shipment directly to the subject via courier within one business day of subject enrollment notification. The site will call the subject daily until receipt of the device is confirmed by the subject and instruct the subject to register the device by following the set-up instructions in the package and contacting ZOLL technical support for final instruction and initiation of the device.

Sites Located Outside the United States

For sites outside the United States, the investigator will be responsible for dispensing the study device and making necessary requests to the sponsor when inventory is low.

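### Section 8.4 compares device readings at the time of heart failure admission but gives event-free subjects no day on which to be read

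*Combined protocol and SAP*

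**What the plan says.** Secondary endpoint 8.3.2.1 is the strength of association between device measurements and heart failure events (objective 2.2.1). Section 8.4 names a sensitivity/specificity analysis and a group comparison. The comparison is made at two times: the first day of fitting, and "the time of heart failure admission will be compared among subjects with or without heart failure related events using t-tests". A closing clause allows another suitable method.

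The sections that bear on the second time point are these.

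- **Start of readings.** In 3.1.1 the device "fitting will mark day 0 of the study", at or within 10 days after the index discharge. For US sites, 7.3.1 says: "The sponsor will initiate a device shipment directly to the subject via courier within one business day of subject enrollment notification".
- **What counts as an event.** Section 6.1.3 defines it as a "hospitalization, emergency room visit, observation unit visit, or unplanned clinic visit where medical management or treatment for HF related pulmonary congestion is administered".
- **How long events are collected.** Section 3.1.1: "The weekly phone calls will continue if the subject has stopped wearing the device". In 6.4, calls at six months and one year are made "to assess for mortality status, heart failure related clinical events that have occurred since the end of" wear.
- **Extended wear.** All subjects may choose a further 90 days. Under 6.2.4.7, after an event in the previous 90 days, "the subject will also be given the option to continue wear for 30 days following the most recent heart failure event".
- **Gaps in the data.** Section 8.6.3 rules out replacing missing data. Section 8.5 is marked not applicable.

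**The concern.** A two-group test needs a reading from each group. Subjects without an event have no admission during wear, and the index stay cannot supply one because wear starts at or after discharge. No section gives them a matched wear day, a fixed study day, a last wear day or an average over wear.

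Two further gaps concern the groups. If admission is read literally, a subject whose event was an emergency room, observation unit or unplanned clinic visit also has no such time. And a subject whose only event came after wear ended has an event but no reading at it; the plan does not say in which group that subject belongs.

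At stake is the estimate itself. If readings drift with time since discharge, controls read earlier or later than the cases differ from them for that reason alone, and the result could be taken as evidence for or against the device's association with events.

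**Working it through.** **Figures in the plan.** There is none to reproduce: the documents give no alpha, effect size, SD, event rate or drift for this analysis. Only the sample size of 300 (5.2, 8.1) and the 90-day wear (3.1.1) come from the plan. All other inputs below are assumptions, and 5% is only a yardstick.

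**Closed form, no true association.** Let readings have SD 1 on every day and a common linear drift of d SD over 90 days. Let event days be uniform, with mean 45, and read all controls on day c (first day taken as 0).

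- Expected difference, event minus event-free: d × (45 − c)/90.
- With d = 0.5: first day, 0.5 × 45/90 = +0.25 SD; day 90, 0.5 × (−45)/90 = −0.25 SD; day 30, 0.5 × 15/90 = +0.083 SD; day 45, 0. A falling drift reverses the signs.
- Variance in the event group: 1 + 0.5²/12 = 1.021. With 75 event and 225 event-free subjects, SE = √(1.021/75 + 1/225) = 0.134.
- First day or day 90: z = 0.25/0.134 = 1.86, so the chance of |z| > 1.96 is about 46%. Day 30: z = 0.62, about 9.5%.

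**Simulation.** Welch test, 4,000 replicates per cell, AR(1) 0.9 daily series, events independent of readings, 75 events, uniform event days. Rejection in %:

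| Controls or method | d = 0 | 0.3 | 0.5 | 1.0 |
|---|---|---|---|---|
| First day | 4.7 | 19.8 | 43.9 | 95.0 |
| Day 30 | 4.8 | 6.7 | 9.5 | 24.6 |
| Day 45 | 4.7 | 5.0 | 4.7 | 4.8 |
| Day 60 | 5.0 | 6.5 | 9.7 | 21.2 |
| Day 90 | 4.9 | 18.8 | 46.9 | 94.8 |
| Subject mean | 5.1 | 4.9 | 4.5 | 4.9 |
| 1:4 risk-set conditional logistic | 5.1 | 4.7 | 4.7 | 4.9 |
| Time-varying Cox, robust errors | 5.2 | 5.7 | 5.2 | 5.2 |

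Separate simulations with slightly different set-ups put the two extreme choices at 44 to 48% for a 0.5 SD drift. With 45 or 105 events at that drift, first-day controls give 32.6 and 52.7%, day-90 controls 32.3 and 53.1%.

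**Event timing.** Mid-period controls are safe only because uniform event days average 45. If events are front-loaded (truncated exponential, scale 30 days), the mean event day is 30 − 90 × e⁻³/(1 − e⁻³) = 25.3. Day-45 controls then give 0.5 × (25.3 − 45)/90 = −0.11 SD. Simulated rejection at d = 0.5 is 17.6% (first day), 5.3% (day 30), 12.7% (day 45), 76.0% (day 90), 14.3% (subject mean), 5.3% (conditional logistic) and 5.7% (Cox).

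**Limit of the matched analyses.** Over all 22 cells run, conditional logistic gave 4.3 to 6.2% and Cox 5.2 to 6.2%. Every one of those cells made events independent of readings. In this study a data update, triggered by high readings, can lead to an office visit, ED visit or hospitalization (3.1.1, 6.3.1, 6.3.4) that may meet 6.1.3. A driftless null simulation (300 subjects, 1:4 risk sets, 1,000 replicates) gave:

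| Triggered events (mean) | Background events | Triggered share | Rejection |
|---|---|---|---|
| 0 | – | 0% | 5.3% |
| 1.5 | 72 | 1.5/73.5 = 2.0% | 10.8% |
| 3.2 | 70 | 3.2/73.2 = 4.4% | 22.0% |
| 7.7 | 65 | 7.7/72.7 = 10.6% | 59.2% |

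A second simulation gave 28% with about 5 triggered events. The bias is upward. The numbers of triggered events are assumed.

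**The case against.** **Admission may be loose wording for any 6.1.3 event.** Criterion 4.1.2 supports this: "This acute heart failure event admission must be at least 2 weeks apart from the event admission in 4.1.1", although the earlier event there need not be a hospital stay. That would settle the day for event subjects. Event-free subjects would still have none.

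**Another method is allowed.** It is, and a sound analysis is therefore permitted. But no choice of test supplies the day on which controls are read.

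**The sentence may mean baseline against admission within event subjects.** Its wording compares subjects with and without events, so that reading does not fit.

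**The large error rates need extreme control days and an assumed drift.** This stands. The first day is already the plan's separate baseline time point, so reusing it as the admission day is unlikely. A reader might infer that the planned analysis has a false-positive rate near one half; the documents do not support that. A drift is plausible, since subjects enrol soon after decompensation and sites may change treatment in response to readings, but no size is given. Equal variance on every day is also assumed, although TFI is normalized to a baseline (1.1).

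**Deliberate choice of day.** A reader might infer that the sponsor means to choose the control day after looking at the data. The plan only leaves the day unstated.

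**Events after wear.** These cannot enter as cases, since no reading exists and none is imputed. Only the group of those subjects is unclear.

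**Matching on wear day may seem to cure everything.** It does not. An event brought about by a data update is a case because its reading was high, and matching cannot remove that circularity.

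**Conclusion.** The gap is certain on the text: the comparison at the second time point cannot be run as written. Its numerical effect is conditional. With a common drift of 0.5 SD over 90 days and 75 uniformly timed events among 300 subjects, the control day moves the estimate between about +0.25 and −0.25 SD when the truth is 0; with no drift it does nothing. The same-day matched analyses keep error at about 5 to 6% only when events do not depend on readings.

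This should be fixed, but its reach is limited. It concerns one of two analyses named for a secondary association endpoint in a non-randomized study, with no stated alpha or decision rule. A reader might infer that the study's main conclusion is at risk; it is not, because the primary engagement endpoint and the safety endpoint do not use this comparison.

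Not simulated: the censoring rule proposed below, wear beyond day 90, repeat events, and wear loss related to the reading.

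**What to change.** Before the data are examined, replace the t-test at the second time point and state the following.

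1. **Case reading.** Use each event subject's reading on or just before the first 6.1.3 event during the initial 90-day wear. State the look-back window and the handling of repeat events.
2. **Comparators.** Use subjects event-free and still wearing the device on the same wear day, by risk-set matching with conditional logistic regression, or by a Cox model with the daily measurement as a time-varying covariate and subject-robust errors.
3. **Window.** Count only events during the initial wear, and say how subjects with later events are classified. Extended wear is best left out of the main analysis: later comparators would come only from subjects who chose to continue, and the 30-day option is open only after an event.
4. **Events resulting from a data update.** Section 6.3.1 already classes these as unscheduled events. Identify them, exclude them as cases in the main analysis by censoring at the data update, and include them in a sensitivity analysis. Say whether subjects whose update led to no event are also censored.
5. **Stated limit.** Treatment changes after a data update may weaken the association.

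The cost is SAP wording and modest programming, since daily data are already transmitted (7.1). Some events will lack a usable reading. Section 7.1 anticipates wear above 70%. As an illustration, if 60% of subjects stopped on a uniformly random day, mean wear would be 0.4 + 0.6 × 0.5 = 70%, and about 0.70 × 75 ≈ 53 of 75 events would have one. Censoring at data updates would reduce this further.
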